10.4. VBG Analysis (for Hospitalized Participants Only)

VBG will only be assessed in hospitalized participants. VBG analysis will be as outlined in the SoA (Table 5) and measurements will include pH, partial pressure of oxygen, partial pressure of carbon dioxide, oxygen saturation, and the bicarbonate (HCO_3^-) concentration.

10.5. Patient-reported Outcome Questionnaires

Patient reported outcomes (PRO) data will be captured electronically using a handheld device at home and at the site. Site personnel will be trained on the use of the device and detailed procedures for using the device will be described in a separate instruction manual.

Participants will be trained on home use of the e-diary at Visit 2 and throughout the trial on an as needed basis. Training will emphasize the importance of completing the PRO assessments as scheduled to capture the participant's experience and meet the objectives of the trial.

The participant will complete the following assessments daily via the e-diary at the timepoints defined per the SoA to:

- Respond to the COPD exacerbation and symptom scale questions of the Exacerbations of Chronic Obstructive Pulmonary Disease Tool (EXACT)-PRO tool every evening (typically at bedtime).
- Respond to Dyspnea Numerical Rating Scale (NRS) twice daily.
- Record use of short-acting rescue medications twice daily.

Investigator/authorized delegate will check participant's adherence to the PRO assessment schedule as is necessary and at each trial visit to minimize missing data.

The other questionnaires, the COPD Assessment Test (CAT) (see Section 10.5.1) and the St. George's Respiratory Questionnaire (SGRQ) (see Section 10.5.2), will only be administered at on-site visits or telephone call visit as outlined in the SoA (Table 5). Participants responses to the questionnaires will be captured electronically using a handheld device at the site with the

exception of using paper CAT questionnaires at the telephone call visit (Visit 7). Electronic upload of a participant completed paper questionnaire is permitted when use of the electronic questionnaire is not possible.

For participants who are hospitalized, if a participant is too ill to complete the PRO questionnaires without assistance on a given day, a member of the trial staff may verbally recite the questions verbatim to the participant and the staff member may enter the participant's verbal response in the e-diary. The participant's confirmation of the accuracy of the staff member's transcription will be documented in the source document/e-diary. As the PROs are validated for self-administration only, the reason for this deviation will also be recorded. Hospitalized participants will be encouraged to complete the e-diary personally as soon as possible and will be trained to do so before discharge.

PRO questionnaires should be completed prior to any other assessments or procedures per visit. Participants should complete the CAT at relevant trial visits per the SoA prior to performing any other trial procedures (including concurrent medication assessment, AE assessment, clinic spirometry, etc.), and prior to completion of the SGRQ. However, during the Screening Visit (Visit 1b) and/or the Randomization Visit (Visit 2), this order may be modified as needed, including instances where some or all of these procedures are performed as part of routine/urgent/inpatient hospitalized care.

10.5.1. COPD Assessment Test

COPD-related health status will be assessed using the COPD Assessment Test (CAT) (Jones et al. 2009; Jones et al. 2012); see Appendix G. The CAT (www.CATestonline.org) is a validated, short and simple patient-completed questionnaire, which has been developed for use in routine clinical practice to measure the health status of patients with COPD. The CAT is designed to measure overall COPD-related health status for the assessment and long-term follow-up of individual patients. The CAT is an 8-item questionnaire suitable for completion by all patients diagnosed with COPD. When completing the questionnaire, participants rate their experience on a 6-point scale, ranging from 0 (no impairment) to 5 (maximum impairment) with a scoring range of 0 to 40 (Jones et al. 2009; Jones et al. 2012).

10.5.2. St. George's Respiratory Questionnaire

The St. George's Respiratory Questionnaire is a 50-item questionnaire designed to measure and quantify health status in adult patients with chronic airflow limitation; see Appendix F (Jones et al. 1991; Jones et al. 1992). A global score ranges from 0 to 100. Scores by dimension are calculated for 3 domains: Symptoms, Activity and Impacts (Psycho-social) as well as a total score. Lower score indicates better quality of life.

The first part ("Symptoms") evaluates symptomatology, including frequency and severity of cough, sputum production, wheeze, breathlessness and the duration and frequency of attacks of breathlessness or wheeze. The second part has 2 components: "Activity" and "Impacts".

The "Activity" section addresses disturbances to a participant's daily physical activities.

The "Impacts" section covers a range of effects that chest troubles may have on a participant's daily life and psycho-social functions (eg, daily life activities and functioning, employment, physical functioning, emotional impact, stigmatization, and a participant's perceptions when treated). The recall period of the questionnaire is over the past 4 weeks.

Psychometric testing has demonstrated its repeatability, reliability and validity. Sensitivity has been demonstrated in clinical trials. A minimum change in score of 4 units was established as clinically relevant after patient and clinician testing. The SGRQ has been used in a range of disease groups including asthma, COPD, and bronchiectasis.

10.5.3. Dyspnea Numerical Rating Scale

Daily dyspnea intensity will be evaluated by having the participant respond to the question “How much shortness of breath you are having right now?” twice a day (within 30 minutes of waking up [morning] and going to bed [evening], while they are resting) in e-diary with a 0 to 10 NRS; see [Appendix E](#). Participants will be asked to rate their shortness of breath by circling a number from 0 to 10, with 0 being no shortness of breath and 10 being shortness of breath as bad as it can be.

The Rome Proposal of COPD exacerbation reached a consensus to recommend the visual analog scale to quantify the severity of the resting dyspnea in patients with COPD ([Celli et al. 2021](#)), which has been validated against ventilatory loads ([Gift and Narsavage 1998](#)), can be represented by a numerical scale from 0 to 10 ([Gift and Narsavage 1998](#)), and has a minimally clinical important difference of 1 ([Ekstrom et al. 2020](#)). The NRS is a valid measure of present dyspnea in COPD patients which was supported by the high correlation of its scores with scores from the Dyspnea Visual Analog Scale.

10.5.4. Exacerbations of Chronic Pulmonary Disease Tool

Exacerbations of Chronic Pulmonary Disease Tool – Patient-Reported Outcome (EXACT-PRO) is a PRO instrument designed to capture information on the occurrence, frequency, severity, and duration of exacerbations of disease in patients with COPD ([Leidy et al. 2011](#); [Leidy et al. 2014](#)). EXACT-PRO captures information on the severity of the respiratory and systemic manifestations of a COPD exacerbation as reported by the patient ([Leidy et al. 2011](#)). Development and validation history of the tool is consistent with guidelines proposed by the FDA, European Medicines Agency (EMA), and well-known measurement principles.

The instrument is a daily diary composed of a total of 14 items representing the following domains:

- Breathlessness (5 items),
- Cough and sputum (2 items),
- Chest symptoms (3 items),
- Difficulty bringing up sputum (1 item),
- Tired or weak (1 item),
- Sleep disturbance (1 item), and
- Scared or worried (1 item).

The instrument is to be completed every evening (typically at bedtime) using an e-diary. However, at Visit 2 (Randomization) only, the EXACT-PRO is to be completed as the first assessment before randomization and hence can be completed in the morning or afternoon. The daily recording of information allows an assessment of the underlying day-to-day variability of a

participant's symptoms and facilitates the detection of symptom worsening indicative of a COPD exacerbation. The total score for EXACT-PRO ranges from 0 to 100. The EXACT total score assesses COPD exacerbations. The higher the score, the more severe are the symptoms.

The Evaluating Respiratory Symptoms in COPD (E-RS: COPD) consists of 11 items from the 14-item EXACT-PRO instrument. E-RS: COPD is intended to capture information related to the respiratory symptoms of COPD (ie, breathlessness, cough, sputum production, chest congestion, and chest tightness). The E-RS has a scoring range of 0 to 40 (Leidy et al. 2014). Three subscales of the E-RS: COPD are used to describe different symptoms; dyspnea, cough and sputum and chest symptoms.

In addition to the collection of EXACT-PRO, participants will also complete daily e-diary questions to provide information on other symptoms suggestive of exacerbation, such as sputum purulence (color), wheezing, sore throat, colds (nasal discharge and/or nasal congestion), and fever without other cause.

10.5.5. Rescue Medication Use

Use of rescue medication (albuterol [salbutamol]) including inhaler and nebulizer use will be captured twice daily in the e-diary.

Inhaler usage will be reported as the number of puffs (ie, the sum of different relievers, if applicable) in a given period whereas nebulizer use will be reported as the number of times.

Rescue medication usage at night will be assessed in the morning and rescue medication used during the day will be assessed in the evening. For participants who are hospitalized and/or if the participant is too ill to complete the e-diary on his/her own on a given day, a member of the trial staff may enter the participant's use of non-nebulized rescue medication and/or the number of nebulized treatments over the given period in the e-diary, as applicable. The participant's confirmation of the accuracy of the staff member's transcription will also be documented in the e-diary/source document.

10.6. Healthcare Resource Utilization and Economics

A questionnaire of health care resource utilization (physician visit, hospitalization, ICU admission, emergency or urgent medical care facility visit) will be collected by the Investigator for all participants throughout the trial.

The data collected will include:

- Reasons and duration of hospitalizations and ED visits.
- Length (hours) of stay in ED per visit.
- Unscheduled visits for urgent care primarily related to COPD symptoms.
- Total length (hours) of stay in ED over the 28-day Treatment Assessment Period.
- ICU admission rate.
- Time to ready-for-discharge in hospitalized participants based on clinical assessment and lung function tests.

The data collected will exclude procedures, tests, and encounters mandated by the protocol.

10.6.1. Time to Ready-for-Discharge in Hospitalized Participants

For hospitalized participants, Investigators or their designees will assess participants daily during the initial hospitalization against the pre-defined discharge criteria based on clinical assessment (eg, normalization of acidosis, symptoms returning to manageable levels). The time required to meet these criteria will be used to evaluate the speed of initial recovery from COPD exacerbation in hospitalized participants.

This assessment applies only to hospitalizations due to the initial COPD exacerbation and is not applicable to hospitalizations resulting from subsequent COPD exacerbations.

11. ASSESSMENT OF SAFETY

11.1. Screening and Eligibility Assessments

Participants who consent to participate in the trial while in a stable condition should complete Screening Visit 1a after providing written informed consent and after their eligibility has been verified. Investigators or their designees will contact the participants by telephone approximately every 4 weeks after Screening Visit 1a to collect any changes in concomitant medications and any SAEs. If a participant's symptoms worsen, such as increased breathlessness, cough, wheeze, chest tightness, sputum production, or sputum discoloration, this may indicate that the participant is experiencing an exacerbation. Participants should be reminded to contact the site to report worsening symptoms at the onset of the exacerbation, before taking any medication. They should then visit the ED or urgent healthcare clinic associated with the trial center to complete Screening Visit 1b (exacerbation visit) and further verify eligibility criteria. Written informed consent, HIPAA authorization, participant demographics, and previous medical and surgical history will not be collected again at Screening Visit 1b. However, medical conditions that started after Screening Visit 1a should be collected.

For participants who consent to participate in the trial during an urgent healthcare visit for an acute COPD exacerbation, Screening Visit 1b should be completed immediately after providing written informed consent and verifying eligibility.

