8.2.2. Permitted Concomitant Therapy

8.2.2.1. COPD Medications and Non-Drug Therapies

To be eligible to be randomized in this trial, participants must present with an acute COPD exacerbation characterized by an eosinophilic phenotype and required systemic corticosteroids as SoC treatment in the urgent healthcare setting for the acute exacerbation. SoC for the index acute exacerbation is defined for this protocol as treatment with oral/systemic corticosteroid[s] (40 mg/day prednisone or equivalent) for 5 days with or without antibiotic(s) for 7 days; the modification of the dose and/or duration of prednisone (40 mg/day or equivalent) and/or the antibiotic is not recommended but may be allowed according to the Investigator's/medically qualified designee's judgement.

The start of SoC is defined as the start of either oral or systemic corticosteroids(s) or antibiotic(s), whichever is earliest.

Note: SoC must be documented in the participant's source documentation and in the eCRF. The use of other medications for treatment of the index acute COPD exacerbation and any subsequent COPD exacerbation(s), if applicable, is at the discretion of the Investigator or medically qualified health care personnel. Use of medication for treatment of subsequent exacerbations does not need to follow the SoC requirements for the index acute exacerbation.

In addition, participants are instructed to continue their regular COPD maintenance treatments (eg, LAMAs, LABA/ICS combinations, LABA/LAMA combinations, or LABA/LAMA/ICS combinations) for the duration of the trial. However, participants must withhold the morning dose of usual scheduled COPD medications on the morning of the spirometry assessments, except when treatment is needed for an acute COPD exacerbation.

Note: Modification(s) of the dosing regimen for the regular COPD maintenance treatments is(are) permitted as deemed medically appropriate by the Investigator/medically qualified designee; the modifications will be recorded in source documents and eCRF.

Other concomitant COPD maintenance medications may be allowed at the discretion of the Investigator following consultation with the Sponsor Medical Monitor, with the exception of short-acting anticholinergics for use as rescue medication.

Oxygen for intermittent use or PRN therapy ≤ 15 hours per day is allowed. LTOT or nocturnal oxygen therapy required for >15 hours is excluded throughout the trial.

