8.2.2.3. Rescue Therapy

The trial site will supply each randomized participant with albuterol [salbutamol] metered dose inhaler (MDI) for use in performing the post-BD FEV₁ assessments and as rescue medication for use as needed throughout the trial for treatment of acute symptoms of COPD.

A participant may use a different short-acting β -agonist (SABA) inhaler other than that provided (eg, a different brand of albuterol/salbutamol/ levalbuterol that is distributed at Screening). All SABA inhaler dosing (puffs) must be recorded in the daily e-diary.

In addition, rescue use of albuterol (salbutamol) nebulized administered via nebulization is discouraged, except as urgent treatment during a COPD exacerbation. Occasions where SABA is administered via nebulization will be recorded separately from metered dose inhaler inhalations in the e-diary. Use of low dose ICS-formoterol as rescue medication is not allowed during the trial.

Although the use of rescue albuterol (salbutamol) medications is allowable at any time during the trial, its use should be delayed for at least 4 hours prior to completing the pre-BD spirometry

assessments, unless required for treatment of an acute exacerbation COPD. It is anticipated that participants who are randomized into the trial will receive albuterol as part of the routine treatment of the acute COPD exacerbation during Visit 1b and Visit 2. In this instance spirometry should be scheduled to coincide with this treatment to allow post-BD recordings to be measured.

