ADA = anti-drug antibodies; AE = adverse event; AESI = adverse event of special interest; β -hCG = human chorionic gonadotropin-beta; BD = bronchodilator; CAT= COPD Assessment Test; COPD = chronic obstructive pulmonary disease; CT = computed tomography; D = day; ECG = electrocardiogram; ED = emergency department; e-diary = electronic diary; EOT = End of Trial; EXACT PRO = Exacerbations of COPD Tool – Patient-Reported Outcome; FeNO = fractional exhaled nitric oxide; FEV₁ = forced expiratory volume in 1 second; HIPAA = Health Insurance Portability and Accountability Act; ID = identification; IP = investigational product; LABA = long-acting β 2-adrenergic agonists; LAMA = long-acting muscarinic antagonist; MDI = metered dose inhaler; nAb = neutralizing antibody; NRS = Numerical Rating Scale; PARC = pulmonary and activation-regulated chemokine; PK = pharmacokinetic(s); PRN = pro re nata; SABA = short-acting β -agonists; SAE = serious adverse event; SGRQ = St. George's Respiratory Questionnaire; V = visit

Note: Participants will be monitored at the trial site for a minimum of 2 hours after IP administration.

a According to the timepoint at which participants consent to the trial, the Screening procedure will be as follows:

- For participants who consent to participate in the trial while in a stable condition, they should complete Visit 1a after providing written informed consent and eligibility has been verified. Investigators or their designees will contact the participants by telephone approximately every 4 weeks after Visit 1a to collect any changes in concomitant medications and any SAEs. If a participant's symptoms worsen, such as increased breathlessness, cough, wheeze, chest tightness, sputum production, or sputum discoloration, this may indicate that the participant is experiencing an exacerbation. Participants should be reminded to contact the site to report worsening symptoms at the onset of the exacerbation, before taking any medication. They should then visit the ED or urgent healthcare clinic associated with the trial center to complete Visit 1b (exacerbation visit) and further verify eligibility criteria. Written informed consent, HIPAA authorization, participant demographics, and previous medical and surgical history will not be collected again at Visit 1b. However, medical conditions that started after Visit 1a should be collected.

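### The call-first reminder at exacerbation onset covers every medication, so read literally it delays the rescue inhaler with no stated eligibility or baseline purpose

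*Protocol*

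**What the plan says.** Section 11.1 describes what happens between Screening Visit 1a and Visit 1b for participants who consent while stable. It lists signs that an exacerbation may have begun, among them breathlessness, wheeze and chest tightness. It then says participants should be reminded to "contact the site to report worsening symptoms at the onset of the exacerbation, before taking any medication", and directs them to the emergency department or urgent healthcare clinic for Visit 1b. Footnote a of the Schedule of Assessments in Appendix A carries the same sentence: "Participants should be reminded to contact the site to report worsening symptoms at the onset of the exacerbation, before taking any medication". Neither place makes an exception for a reliever.

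Section 8.2.2.3 takes a permissive line on the reliever: "Although the use of rescue albuterol (salbutamol) medications is allowable at any time during the trial". The same sentence asks for a delay of at least 4 hours before pre-bronchodilator spirometry and lifts that delay where albuterol is "unless required for treatment of an acute exacerbation COPD". Nebulized albuterol "is discouraged, except as urgent treatment during a COPD exacerbation". The section also anticipates that randomized participants "will receive albuterol as part of the routine treatment of the acute COPD exacerbation during Visit 1b and Visit 2".

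**The concern.** The reminder operates at the moment a participant becomes more breathless, which is when a reliever is meant to be used. A site that relays the sentence word for word would be asking the participant to telephone before using the inhaler. The stake is an avoidable delay in symptom relief for participants in the stable channel. It is a matter of participant safety and of consistency between sections, not of inference from the trial data.

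**Working it through.** No arithmetic beyond counting applies, and the plan gives no figure to reproduce. The check sets the relevant provisions side by side.

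**1. Scope of the reminder.** It appears in 2 places (Section 11.1 and footnote a). Places that exempt the reliever: 0 of 2. Section 6.1 gives a similar reminder to contact the site but says nothing about medication, so it neither supports nor contradicts the wider wording.

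**2. Does the reliever permission reach Screening?** This takes some inference.
- In favour: Section 6.4 counts the Screening Period of up to 26 weeks in the duration of the trial. Section 8.2.2.3, in allowing a different short-acting inhaler, refers to "levalbuterol that is distributed at Screening".
- Against: the sentence on inhaler supply in Section 8.2.2.3 concerns randomized participants. The permission itself opens a sentence about pre-bronchodilator spirometry, which Section 10.3 places at Visits 6, 8 and 9 and at hospital discharge, all after randomization.

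On balance the permission reasonably covers Screening, but the text does not say so outright.

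**3. Does any stated purpose need the reliever to wait?**

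| Provision | What it concerns | Needs reliever withheld? |
|---|---|---|
| Note to inclusion 11 | Eosinophil count before corticosteroids, advisory | No |
| Exclusion 20, with the definition of SoC start in Section 8.2.2.1 | More than 48 hours since corticosteroids or antibiotics began | No |
| Baseline FEV1 (Section 10.3) | Post-bronchodilator value at Visit 2 before dosing | No |
| Treatment around Visits 1b and 2 (Section 8.2.2.3) | Albuterol expected as routine care | No |

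The timing provisions concern 2 drug classes, systemic corticosteroids and antibiotics. The reminder covers all drugs.

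**4. How the protocol words comparable limits.** Four limits on inhaled therapy state an exception for an acute exacerbation:
- the withheld morning maintenance dose (Section 8.2.2.1)
- the 4-hour albuterol delay (Section 8.2.2.3)
- nebulized albuterol (Section 8.2.2.3)
- short-acting anticholinergics (Table 3)

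The pattern is not universal. The pre-bronchodilator washout in Section 10.3 depends on tolerance, and ICS-formoterol as rescue is simply not allowed. Still, the reminder applies only at exacerbation onset and carries no exception.

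**The case against.** The strongest reply is that nothing is contradicted. The sentence asks the participant to call first and prohibits nothing, and calling first is compatible with permission to use albuterol. Context also narrows it: inclusion criterion 10 defines an exacerbation by symptoms that lead to a change of medication, so the natural reading is medication newly taken for the exacerbation. The next sentence sends the participant to urgent care. The four exceptions listed above can be read as showing that the protocol does not mean to block needed treatment. What participants are actually told is not shown, so the harm is hypothetical.

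Much of this stands. The reminder is an order of steps, its likely intent is narrower than its words, and the harm cannot be sized. What remains is that neither place states the narrower intent, and this is the sentence sites are asked to pass on. A statistician can infer the intent; a breathless participant may not.

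A reader might go further and infer a conflict with Section 8.2.2.1, under which "participants are instructed to continue their regular COPD maintenance treatments". The document does not support that. Regular doses are already being taken and are not started for the exacerbation, and at most a scheduled dose would wait until the call. A reader might also infer a ban on rescue use during Screening; the text sets a sequence and bans nothing.

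**Conclusion.** The point holds for the reliever only. As written, the reminder is broader than any purpose the protocol states, and read literally it sits badly with Section 8.2.2.3. It is a loose instruction, not a flat contradiction.

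Its size is small: one sentence in 2 places, acting only at exacerbation onset in participants who consented while stable. The number affected and the length of any delay cannot be derived from the document. Sample size, alpha and the primary analysis are unaffected.

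The conclusion rests on two assumptions: that the permission for rescue albuterol extends to Screening, and that some sites may relay the sentence literally. If the first fails, the tension with Section 8.2.2.3 weakens, but the absence of any stated reason to hold back the reliever remains.

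**What to change.** In Section 11.1 and in footnote a of the Schedule of Assessments, replace the clause after the comma with: *before starting systemic corticosteroids or antibiotics for the exacerbation, where possible; use of the rescue inhaler should not be delayed*. The sentence may add that regular maintenance treatment continues. The qualifier on feasibility matches the note to inclusion criterion 11. The sponsor's clinicians should confirm the wording, and participant-facing instructions should follow it.

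The cost is one sentence in two places. Eligibility criteria, visits, sample size and analysis stay as they are, and the prompt to call first is kept for the drug classes that matter to eligibility.
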